## Abbreviations

BMI	Body mass index
CBT	Cognitive behavioral therapy
HbA1c	Glycemic control
L2B	Learning 2 Breathe
MBI	Mindfulness-based intervention
T2D	Type 2 diabetes

### 1.0 Background and Rationale

The obesity epidemic is associated with an increase in youth-onset type 2 diabetes (T2D), as well as its precursor condition, prediabetes. Approximately, 20% of youth, ages 12-18 years old, have prediabetes. If prediabetes progresses to T2D, glycemic control is often more difficult to achieve in youth as compared to adults. Poor glycemic control is associated with diabetes-related complications and decreased life expectancy. This is especially troubling as obesity and T2D disproportionately affect youth from marginalized and minority race/ethnicity backgrounds who often face additional stressors and barriers to diabetes care. Effective patient-centered, holistic treatments are needed for youth with prediabetes or T2D.

Mindfulness-based interventions (MBI) may offer additional benefits to traditional health care for youth living with prediabetes or T2D. Mindfulness refers to non-judgmental, focused attention on the present moment. MBIs teach skills to increase present moment attention and adopt a nonjudgmental attitude towards one's experience which can foster healthy stress coping behaviors and greater self-regulation; both of which are associated with improved diabetes self-care behaviors. MBIs were introduced to the clinical population in the 1970's and have been translated for a variety of populations and health conditions including diabetes.

A systematic review and meta-analysis of eight RCTs investigated the effect of MBIs on glycemic control (HbA1c) and psychological outcomes (depression, stress, diabetes-related distress, anxiety) in adults with diabetes. The authors found that MBIs had a moderate effect size on decreasing depression and stress, and changes were greatest in individuals with higher baseline psychological symptoms. MBIs were associated with small reductions in HbA1c and diabetes-related distress, but MBIs did not have a consistent effect on anxiety. A longer follow up time (>6 months post baseline) was associated with greater improvements in HbA1c.

Few studies have examined the role of MBIs in adolescents for diabetes prevention and management. Ellis et. al. (2019) conducted a RCT to evaluate the efficacy of a MBI in urban adolescents with poorly controlled type 1 diabetes. Adolescents with a high stress reactivity score at baseline in the MBI group experienced the greatest decreases in HbA1c at 6 months (0.70%) compared to those in the cognitive behavioral therapy (CBT) group (0.35%) and diabetes support group (0.53%). For adolescents with elevated levels of stress, MBI may be beneficial for improving glycemic control.

A RCT compared the effectiveness of a six-week MBI vs a CBT group on depression and insulin resistance in adolescent girls with risk factors for T2D. Depressive symptoms, perceived stress, insulin resistance, and adiposity were measured at baseline, post-intervention, and 6 months. Adolescents in the MBI group had greater decreases in depressive symptoms compared to CBT group at post-treatment and 6 months. The MBI group also had improvements in insulin resistance compared to the CBT group, after controlling for adiposity.

MBIs may be a promising complementary approach for T2D prevention and treatment in youth, and thus, warrant further investigation.

## **2.0 Specific Aims**

We propose a MBI for adolescents with prediabetes or T2D. Specific aims of this proposal include:

**Aim 1: Pilot test the feasibility and acceptability of a mindfulness-based intervention in adolescents with prediabetes or type 2 diabetes.**

**Aim 2: Explore secondary physical and mental health outcomes of the study cohorts.**

Primary outcomes will assess participant adherence to the study protocol and satisfaction with the intervention. Secondary outcomes will preliminarily assess the effect of the intervention on clinical care measures (e.g., HbA1c, BMI) and patient-centered outcomes including quality of life. We will identify factors that support or interfere with the uptake and sustained use of the intervention in the diabetes care context to assist in future multi-site, pragmatic, or implementation science trials. We hypothesize that offering mindfulness-based skills will result in improved outcomes and thus would lead to change in clinical practice to incorporate such teachings.

## **3.0 Inclusion/Exclusion Criteria**

Adolescents between the ages of 12-18 years old who are referred for treatment of prediabetes or T2D are eligible for this study. Participants will have normal cognition and will be English speaking as the group is offered in English. Adolescents are not eligible to participate if they have diagnosed cognitive disability that would prevent participation in a group or if they are unable to attend the MBI group sessions.

Criteria for inclusion:

- Age 12-18 years
- Referred to clinic for treatment of prediabetes or type 2 diabetes
- English speaking

Criteria for exclusion:

- Diagnosed cognitive disabilities
- Inability to attend visits due to individual schedules

## **4.0 Enrollment**

We aim to recruit 50 individuals with the goal of at least 20 participants to complete the study (two groups of 10 participants).

**Recruitment Sites:** Diabetes care providers see patients in an outpatient setting at Riley Specialty Care at IU Health Methodist in Indianapolis, Indiana. Additional outreach clinics available for participant recruitment include Riley Specialty Care at Riley Outpatient Center, IU North, Bloomington, Fort Wayne, and South Bend.

**Recruitment Procedures:** Eligible patients will be recruited in one of the following ways: 1) health care providers will identify eligible adolescents during clinic visits, 2) a letter will be mailed to patients referred for prediabetes or type 2 diabetes who have been seen in one of our clinics within the last 12 months, or 3) a member of the research team will call eligible patients. The letter and phone call scripts are provided in separate documents.

**Consent Procedures:** When a family indicates interest, a member of the research team will initiate contact with the parent or guardian at the end of a clinic visit (if time allows) or by phone. The team member will describe the study, assess eligibility, and answer questions. If the adolescent (and guardian) is willing to participate in the study, the consent process and baseline questionnaires will be completed virtually. The consent process will be based in REDCap. If a family declines participation, they will be asked if they would like to complete the study declination form. This will help to understand reason for disinterest in a MBI.

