## 5.0 Study Procedures

Following enrollment, participants will complete baseline surveys and begin attending the 12-week MBI. Participants will complete surveys following completion of the MBI and at the 12-month follow up. Participants will receive compensation for completing surveys and attending the MBI.

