### Data Collection

**Process Measures:** Intervention fidelity will be assessed with a checklist of session content to ensure that the facilitator is delivering the intervention as intended. Facilitators will follow the manualized curriculum and scripts for mindfulness skills practice.

**Feasibility and Acceptability Measures:** Feasibility and acceptability measures include study participation rate, time to recruit, attendance, study retention rate, study completion rate, data completion, and program acceptability.

**Participant Measures:** Participants will be emailed a link to complete surveys in REDCap. Surveys will be completed at baseline (B), following completion of the MBI at 12-weeks (T1), and at the 12 month follow up (T2). Participants may complete follow-up surveys (12-weeks and 12 months) up to 1 month after the designated time point. A guided interview will also be performed at 12-weeks to receive feedback about the participants' experiences in the study.

Clinical data (HbA1c, BMI, and BMI z-score) will be collected at baseline and at each standard clinical prediabetes or diabetes appointment up to 12 months after the intervention.

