**Table 1. Study Measures**

Feasibility and Acceptability Measures	
Measure	Definition
Study Participation Rate	Number of participants who consented to take part in the study divided by the number of patients approached. We will also document reasons for refusal to participate in the study.
Time to Recruit	Time required to attain the needed sample for each recruitment wave
Attendance	Attendance at each intervention session will be recorded.
Study Retention Rate	Number of participants in a study arm who remain in the study and maintain communication with study staff (regardless of session attendance) divided by the number of participants enrolled in the study.
Study Completion Rate	Number of participants who complete all assessments divided by the number of participants enrolled in the study arm.
Data Completeness	Percentage of questionnaires/study measures completed.
Program Acceptability	Acceptability of the intervention to participants as measured by agreement (on a 5-point likert scale) with different satisfaction measures.

Clinical Measures	
--------------------------	--

Hemoglobin A1c (HbA1c)  
 Body Mass Index (BMI)  
 BMI z-score

*\*When collecting clinical data from prediabetes or diabetes appointments, research team will document any changes to medications that impact glycemia and/or BMI.*

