#### **Intervention:**

The MBI will be conducted in a virtual group setting by Zoom, with a target size of 8-12 participants. Groups may vary in size based on session attendance.

***Mindfulness-based intervention.*** The MBI will follow the Learning to BREATHE (L2B) curriculum. L2B is a manualized 12-week curriculum that teaches a variety of mindfulness skills including breath awareness, body scanning, mindful eating, sitting meditation, loving kindness practice, and mindful movement. Weekly group sessions will last 45-60 minutes. Participants will be invited to engage in daily practice of mindfulness skills (home practice).

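### Nothing limits the time between the baseline survey and session 1, so the pre/post survey change can include an untreated wait that differs between participants.

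*Combined protocol and SAP*

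**What the plan says.** Section 4.0 (Consent Procedures) deals with consent and the baseline surveys together: "the consent process and baseline questionnaires will be completed virtually". Families come in singly, through a clinic visit, a letter or a phone call. The opening of Section 5.0 gives an order of events but no interval: "Following enrollment, participants will complete baseline surveys and begin attending the 12-week MBI".

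The programme is delivered to groups, "with a target size of 8-12 participants" (Section 5.0, Intervention). Table 2 sets out 12 numbered sessions, from a definition of mindfulness to a closing ritual. Recruitment runs in waves. Table 1 makes the time to fill a wave a feasibility measure: "Time required to attain the needed sample for each recruitment wave".

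Section 5.0 (Data Collection) sets a window for the later surveys: "Participants may complete follow-up surveys (12-weeks and 12 months) up to 1 month after the designated time point". It sets none for the baseline survey relative to session 1. The removal rule in Section 7.0, for no communication in the first two weeks, does not limit the wait either. No section provides for a repeat baseline or for recording the wait.

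Section 8.0 compares each participant's baseline with the end of the study by paired t test, for the surveys as well as for HbA1c, BMI and BMI z-score. The protocol describes no control group.

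**The concern.** When individual consent dates lead to one shared start date, participants wait for different lengths of time. If the baseline survey is taken at consent, that wait lies inside the pre/post interval. Depression, anxiety, stress, quality-of-life, mindfulness and emotion-regulation scores can all move over weeks without treatment. With no control group and no term for elapsed time, such movement is counted as change across the intervention. A shift common to most participants biases the mean change. Unequal waits can also add to its spread.

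Section 2.0 wants the secondary outcomes to give a preliminary view of the intervention's effect and to assist later trials. A mean change, and its standard deviation, taken over unequal and unrecorded intervals is a weak input for that purpose.

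**Working it through.** The plan gives no figure for the wait, so there is none to reproduce. The check asks how long it could be.

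**Inputs from the protocol**
- Group size: 8 to 12 (Section 5.0, Intervention); two groups of 10 appear in the completion goal (Section 4.0).
- Programme length: 12 weeks, weekly sessions (Section 5.0, Intervention).
- Recruitment target: 50 (Section 4.0).

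**Assumptions, not in the protocol**
- Recruits enter a wave of size n at a constant rate of r per week.
- Baseline is taken at consent, and session 1 follows when the wave is full.
- T1 falls 12 weeks after session 1.

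**Formulas**
- Wait of the first recruit = (n − 1)/r weeks.
- Mean wait = (n − 1)/(2r) weeks.
- Untreated share of the B-to-T1 interval = wait/(wait + 12).

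**Results for n = 10**

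| r per week | Mean wait (weeks) | First recruit's wait (weeks) | Untreated share, first recruit |
|---|---|---|---|
| 4 | 9/8 = 1.1 | 9/4 = 2.25 | 2.25/14.25 = 16% |
| 2 | 9/4 = 2.25 | 9/2 = 4.5 | 4.5/16.5 = 27% |
| 1 | 9/2 = 4.5 | 9/1 = 9 | 9/21 = 43% |
| 0.5 | 9/1 = 9 | 9/0.5 = 18 | 18/30 = 60% |

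**When the first recruit's wait equals the programme length.** Setting (n − 1)/r = 12 gives r = (n − 1)/12. This is 7/12 = 0.58 per week for n = 8, 9/12 = 0.75 for n = 10 and 11/12 = 0.92 for n = 12. A wait of 12 weeks or more therefore needs slow accrual: for a wave of 10, about 0.75 × 52/12 = 3.25 recruits per month or fewer.

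**If the comparison runs to the 12-month survey (T2).** The end of the study in Section 8.0 could mean T1 or T2. The compensation text places T2 12 months after the intervention, which is 12 + 52 = 64 weeks after session 1. A 9-week wait is then 9/(9 + 64) = 12% of the interval, against 43% for B to T1.

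**Outcomes affected.** The survey baseline is the one placed with consent. HbA1c and BMI come from baseline and routine appointments, and their baseline date is not tied to consent. The primary outcomes in Section 8.0 (attendance, acceptability and interviews) do not use the baseline survey.

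**The case against.** The strongest reply is that the protocol leaves the timing open and does not build in a wait. The Section 4.0 sentence can be read as describing how the surveys are done. Section 5.0 places them after enrolment and beside the start of the programme, and they go out as emailed REDCap links. A link sent shortly before session 1 would fit all of this. This reply stands in part: a long wait is permitted, not prescribed. But the order in Section 5.0 carries no interval, and Section 4.0 puts the questionnaires with consent. If a survey close to session 1 is intended, a sentence should say so.

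A reader might infer three stronger things that the documents do not support.
- **That a group starts only when its wave is full.** Table 1 measures time to recruit but sets no start rule, and 8 to 12 is a target size. The concern does not need this rule: a fixed calendar start with rolling consent also gives unequal waits.
- **That the wait matches the programme in length, so that the interval doubles for the average recruit and triples for the first.** With 25 per wave (50/2) at 1 per week, the mean wait is 24/2 = 12 weeks and the first is 24, giving intervals of 24 and 36 weeks against 12. Neither 25 per wave nor that rate is in the protocol. Mailing and phoning recent patients could fill a wave quickly.
- **That scores would be expected to settle after consent.** Surveys are completed virtually, and Section 3.0 does not select on distress. The direction of any drift is unknown.

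It is also fair to say that an uncontrolled comparison cannot attribute change to the intervention even with a well-timed baseline, and that these outcomes are exploratory. Both limit the stakes. Neither justifies leaving an avoidable and unrecorded interval in the comparison.

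**Conclusion.** The concern holds as a gap in specification. The protocol places baseline surveys with consent, recruits in waves for group delivery, and sets no limit on the time to session 1. The B-to-T1 survey change can therefore contain an untreated wait that differs between participants, and the planned paired t test cannot separate it out.

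The size cannot be fixed from the documents. Under steady accrual into a wave of 10 that starts when full, the mean wait ranges from about 1 to 9 weeks for rates of 4 down to 0.5 per week. The first recruit's wait reaches 12 weeks only at 0.75 per week or slower. At faster rates, the wait is a modest part of the interval.

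The consequence is confined to the exploratory survey outcomes. No feasibility estimate and no sample-size figure changes. It is worth correcting because the correction is cheap.

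**What to change.** - Keep the consent-time survey, so that those who leave before session 1 are still described.
- Re-send the REDCap outcome surveys (PROMIS depression, SCARED-5, PSS-10, PedsQL, MAAS, DERS) before session 1 to anyone whose baseline will be more than 14 days old on that date. The 14 days is a judgement; what matters is that a limit is stated.
- Use the later survey as B in the paired analysis.
- Time T1 from the group's session dates, and state whether the paired comparison runs to T1, T2 or both.
- Report the consent-to-session-1 interval and the losses during it. Table 1 already divides retention and completion by the number enrolled, so those losses are in the denominators; the gain is in showing them separately.

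The cost is a short wording change, a second REDCap link and a repeated survey for some participants. Those who drop out before session 1 may have no baseline inside the window, but their consent-time survey remains.

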## 5.0 Study Procedures

Following enrollment, participants will complete baseline surveys and begin attending the 12-week MBI. Participants will complete surveys following completion of the MBI and at the 12-month follow up. Participants will receive compensation for completing surveys and attending the MBI.

### Data Collection

**Process Measures:** Intervention fidelity will be assessed with a checklist of session content to ensure that the facilitator is delivering the intervention as intended. Facilitators will follow the manualized curriculum and scripts for mindfulness skills practice.

**Feasibility and Acceptability Measures:** Feasibility and acceptability measures include study participation rate, time to recruit, attendance, study retention rate, study completion rate, data completion, and program acceptability.

**Participant Measures:** Participants will be emailed a link to complete surveys in REDCap. Surveys will be completed at baseline (B), following completion of the MBI at 12-weeks (T1), and at the 12 month follow up (T2). Participants may complete follow-up surveys (12-weeks and 12 months) up to 1 month after the designated time point. A guided interview will also be performed at 12-weeks to receive feedback about the participants' experiences in the study.

Clinical data (HbA1c, BMI, and BMI z-score) will be collected at baseline and at each standard clinical prediabetes or diabetes appointment up to 12 months after the intervention.

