**Compensation:**

We will offer \$10, \$25, and \$40 gift cards for the completion of study surveys at baseline (B), the completion of the intervention (T1), and 12 months following the intervention (T2), respectively. We will offer a \$10 gift card per group session for attendance. Participants can earn up to \$195 in total. This is reasonable because the study encourages the practice of the skills outside of the group sessions.

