## **8.0 Statistical Considerations**

Anticipated statistics for this study will be a combination of descriptive statistics and quantitative statistics. For our primary outcomes, we will examine retention and acceptance, as assessed by overall program attendance, program acceptability, and qualitative interviews. Descriptive statistics will include sex, ethnicity, and survey results at B, T1, and T2.

This study includes a post-intervention group guided interview at 12-weeks. The facilitator will ask the group for feedback about the intervention with the following questions: 1) What did you like about participating in this study? 2) What did you dislike about participating in this study? 3) What were your expectations from participating in this study? 4) Were those expectations met?

A paired t test will be used to compare variables of an individual at baseline and at the end of the study (pre/post), including HbA1c, BMI, BMI z-score, and survey results.

This is a pilot feasibility study, therefore there are no data currently available to accurately calculate power. There are no similar studies to substitute such data.

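### Does the lack of a due time for HbA1c and BMI leave the completion measures and the paired t test without a fixed meaning?

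*Combined protocol and SAP*

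**What the plan says.** Surveys have three time points: baseline (B), 12 weeks (T1) and 12 months (T2). Section 5.0 adds an allowance: "Participants may complete follow-up surveys (12-weeks and 12 months) up to 1 month after the designated time point". The Compensation paragraph places the last survey at "12 months following the intervention (T2"). Clinical values follow a different route: they "will be collected at baseline and at each standard clinical prediabetes or diabetes appointment up to 12 months after the intervention".

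Table 1 defines Study Completion Rate as "Number of participants who complete all assessments divided by the number of participants enrolled in the study arm" and Data Completeness as "Percentage of questionnaires/study measures completed". The same table lists HbA1c, BMI and BMI z-score under a separate clinical heading.

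Section 4.0 states: "We aim to recruit 50 individuals with the goal of at least 20 participants to complete the study". The sentence then closes with a bracket naming two groups of ten.

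Section 8.0 uses a paired t test to "compare variables of an individual at baseline and at the end of the study (pre/post), including HbA1c, BMI, BMI z-score, and survey results". Its primary-outcome sentence names attendance, program acceptability and interviews.

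**The concern.** A percentage needs a denominator, and a paired test needs a rule for choosing each member of the pair. For surveys the protocol supplies both. For clinical values it gives no number of expected visits, no window around T1 or T2, no maximum age for the baseline value and no rule for choosing among several values.

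The survey allowance cannot simply be borrowed. It opens 12 months after the intervention, which is when clinical collection closes. Baseline is also loose: consent and baseline questionnaires are virtual, and the letter route reaches patients whose last clinic visit may be up to 12 months old.

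Two of the seven feasibility measures might then take different values from the same records, depending on a choice made after the data are seen. Section 2.0 says the pilot should assist future trials, which plan from such rates. For HbA1c, section 1.0 itself links follow-up beyond 6 months to greater improvement, so it would matter whether the end value lay near T1 or near T2.

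**Working it through.** **Inputs from the protocol.** 50 recruited and 20 completers (4.0); a 12-week course and a one-month survey allowance (5.0); T2 at 12 months after the intervention (Compensation).

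**Assumptions, not in the protocol.** Appointments every m = 3 or 6 months with random timing; share missed q = 0 or 0.2; 20 of 50 finish all surveys; correlation between baseline and end value r = 0.8 or 0.6.

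**The plan's own figure.** 20/50 = 40% completion. No power calculation is stated, so there is nothing else to reproduce.

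**Timing from session 1.** T1 = 12 × 12/52 = 2.77 months. T2 = 2.77 + 12 = 14.77 months. Clinical collection closes at 14.77; the T2 survey allowance runs from 14.77 to 15.77. If a 12-month-old clinic value served as baseline, the longest pre/post gap would be about 12 + 14.8 = 26.8 months.

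**Completion rate under different readings.** The share with a value in a window of w months (w ≤ m) is (w/m)(1 − q). For the last 6 months at m = 3 two visits fall in the window, so the share is 1 − q².

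| Reading | m = 3, q = 0 | m = 6, q = 0 | m = 3, q = 0.2 | m = 6, q = 0.2 |
|---|---|---|---|---|
| Surveys only | 20/50 = 40% | 40% | 40% | 40% |
| Plus any value in the last 6 months | 40% | 40% | 0.96 × 20/50 = 38.4% | 0.80 × 20/50 = 32% |
| Plus a value within 1 month before T2 | (1/3) × 20/50 = 13.3% | (1/6) × 20/50 = 6.7% | 10.7% | 5.3% |

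Only the last row collapses, and its one-month window before T2 appears nowhere in the protocol.

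**Data Completeness for clinical values, q = 0.2.** Against appointments held: 100%, if each yields its values. Against appointments scheduled: 80%. Against B, T1 and T2 with one-month windows and baseline assumed present: (1 + 0.267 + 0.267)/3 = 51% for m = 3, and (1 + 0.133 + 0.133)/3 = 42% for m = 6. Only the first follows section 5.0, which makes values due at each appointment. The third rests on an artificial schedule: a visit at 2.77 to 3.77 months, with exact 3- or 6-monthly spacing, is followed by one at 14.77 to 15.77, outside the window of 13.77 to 14.77. Essentially no one could satisfy both windows.

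**Precision of the paired comparison.** Half-width in SD units = t(0.975, n − 1) × √(2(1 − r))/√n.

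- n = 20: 2.093 × 0.632/4.472 = 0.30 (r = 0.8); 2.093 × 0.894/4.472 = 0.42 (r = 0.6).
- n = 7: 0.58 and 0.83.
- n = 3: 1.57 and 2.22.

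Using the last available value keeps 20 pairs if each of the 20 has at least one later appointment. The counts of 7 and 3 again come from the one-month window (20/3 = 6.7 and 20/6 = 3.3).

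**The wording, side by side.**

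- *Completion.* The opening of section 5.0, Data Collection and Compensation all use completion by participants for surveys. Compensation pays for surveys and session attendance, not for laboratory values. Clinical data are collected by the team from routine care. Table 1's completion rate counts participants who complete assessments, so it reads most naturally as the B, T1 and T2 surveys, which have dates and a window.
- *The 20-completer goal.* The bracket about two groups of ten ties it to the intervention groups, whose target size in section 5.0 is 8 to 12. Nothing ties it to HbA1c or BMI.
- *The end value.* Section 8.0 says "This study includes a post-intervention group guided interview at 12-weeks", which labels the interview. The t test refers to the end of the study, and the last scheduled point is T2.

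**The case for a change.** The best case for a change is that Data Completeness covers study measures as well as questionnaires, so reading the completion rate as surveys only does not settle it. A denominator of appointments held is generous: someone who never returns to clinic adds nothing to it, and the figure can look full while later values are absent. Labels such as baseline and end of the study are also not selection rules. With values at irregular times, one participant's change could span a few weeks and another's up to 26.8 months. A sentence written in advance would cost no visits and no change of test.

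Part of this stands. The clinical denominator is unstated, and so are the maximum baseline age and the end-value rule. The paired comparison will mix follow-up times, which limits what a mean change in HbA1c can show. But these are missing details, not instructions that give a wrong result. The usual choices are the last value before session 1, and the last value or the one nearest 12 months after the intervention. Clinical values come from medical records (9.0), and nothing suggests that their dates would be lost. The number of pairs and the spread of measurement times can therefore be reported with the result. Any narrower window is a trade-off, because it exchanges comparable timing for pairs in a study that expects about 20.

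**Conclusion.** No change to the plan follows. The protocol leaves three details of the clinical data to the analyst: the baseline value, the end value and the completeness denominator. Each has an ordinary answer that fits the text. Study Completion Rate and the 20-completer goal keep a workable meaning as written.

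On the natural reading the implied completion stays at 40%, and the t test keeps up to 20 pairs, with a half-width of 0.30 to 0.42 SD. If any clinical value in the last 6 months also counted, completion would be 32% to 40% under the assumed visit patterns. The much lower figures (5% to 13%, and 3 to 7 pairs) need a window that the plan does not state.

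Little depends on the outcome. Section 2.0 names adherence and satisfaction as primary, section 8.0 uses attendance, acceptability and interviews, and no progression rule uses a clinical value. HbA1c and BMI are preliminary secondary outcomes in an uncontrolled pilot.

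This rests on two assumptions: that the completion rate's assessments are the surveys, and that each survey completer has at least one appointment after the course starts. If the second fails, fewer pairs remain, and the reported count will show it.
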